- 8) Family history of congenital or hereditary immunodeficiency, until the immune competence of the potential vaccine recipient is demonstrated
- 9) Individuals with blood dyscrasias, leukemia, lymphoma of any type, or other malignant neoplasms affecting the bone marrow or lymphatic systems
- 10) Individuals with active tuberculosis
- 11) History of any *Neisseria meningitidis* infection, confirmed either clinically, serologically, or microbiologically
- 12) History of diphtheria, tetanus, pertussis, poliomyelitis, hepatitis B, hepatitis A, measles, mumps, rubella, varicella; and of *Haemophilus influenzae* type b, *Streptococcus pneumoniae*, and /or rotavirus infection or disease
- 13) At high risk for meningococcal infection during the trial (specifically, but not limited to, subjects with persistent complement deficiency, with anatomic or functional asplenia, or subjects travelling to countries with high endemic or epidemic disease)
- 14) History of intussusception

- 15) History of any neurologic disorders, including any seizures and progressive neurologic disorders
- 16) History of Arthus-type hypersensitivity reaction after a previous dose of tetanus toxoid-containing vaccine
- 17) History of Guillain-Barré syndrome
- 18) Known systemic hypersensitivity to any of the vaccine components or to latex, or history of a life-threatening reaction to the vaccine(s) used in the trial or to a vaccine containing any of the same substances, including neomycin, gelatin, and yeast^a
- 19) Verbal report of thrombocytopenia contraindicating intramuscular vaccination in the investigator's opinion
- 20) Bleeding disorder, or receipt of anticoagulants in the 3 weeks preceding inclusion, contraindicating intramuscular vaccination in the investigator's opinion
- 21) Receipt of oral or injectable antibiotic therapy within 72 hours prior to the first blood draw
- 22) Chronic illness that, in the opinion of the investigator, is at a stage where it might interfere with trial conduct or completion^b
- 23) Any condition which, in the opinion of the investigator, might interfere with the evaluation of the study objectives
- 24) Moderate or severe acute illness/infection (according to investigator judgment) on the day of vaccination or febrile illness (temperature $\geq 38.0^{\circ}\text{C}$ [$\geq 100.4^{\circ}\text{F}$]). A prospective subject should not be included in the study until the condition has resolved or the febrile event has subsided

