6.7 Concomitant Medications and Other Therapies

At the time of enrollment, ongoing medications including, but not limited to, other therapies (e.g., blood products), should be recorded in the source documents. All new medications prescribed for new medical conditions / AEs during study participation should also be recorded in the source documents.

Documentation in the CRB of concomitant medication(s) will be limited to specific categories of medication(s) (Categories 1, 2, and 3 as detailed below). Those will include Category 1, 2, and 3 medications ongoing at the time of inclusion in the study, or started at any time during the subject's participation in the trial. For category 3 medication, the period of reporting in CRB will be restricted to only 3 days (72 hours) prior to each blood sampling time point.

Collection Period in Source Documents

Reportable medications (Category 1, 2, and 3) will be collected in the source documents from the day of first vaccination to the end of the trial.^a

Categories of Reportable Medications and Reporting Period

Reportable medications include medications that impact or may impact the consistency of the safety information collected after any vaccination and/or the immune response to vaccination.

Category 1: Reportable medications with potential impact on the evaluation of the safety of the study vaccines. For example, antipyretics, analgesics, non-steroidal anti-inflammatory drugs (NSAIDs), systemic corticosteroids (therapy duration less than 2 weeks), and other immune modulators. Category 1 medications do not define the Per-Protocol Analysis Set (PPAS).

Note: Topical steroids (inhaled, otic, ophthalmic, nasal etc.) should not be captured or reported.

Category 1 medications will be reported in the CRB from the day of first vaccination to the end of the solicited and unsolicited follow-up period after each vaccination. These medications will also be collected in the CRB for the 30-day period prior to the subsequent doses of the vaccine,

^a Subject's parents will be required to document all medications received in the Diary Cards. The sites will focus on only recording the medications belonging to the 3 categories in the other source documents.

wherever applicable (second, third, fourth, etc., in case of a multi-dose schedule with more than a 30-day interval between doses).

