- Category 2: Reportable medications with potential impact on immune response of the study vaccines and used to define the PPAS. For example:
 - Flu vaccines administered within 14 days pre or post each trial vaccination, including the day of the study vaccination visit
 - Any vaccine other than study vaccines (vaccines non-described in the Protocol) within the 28 days (4 weeks) preceding or after the trial vaccination, including the day of the study vaccination visit.
 - Immune globulins, blood or blood-derived products: used in the 3 months preceding the first blood draw and up to the last blood draw
 - Immunosuppressive therapy such as immune-suppressors, immune-modulators with immunosuppressive properties, long-term systemic corticosteroids therapy (prednisone or equivalent for more than 2 consecutive weeks) within past 3 months, anti-cancer chemotherapy, anti-proliferative drugs such as DNA synthesis inhibitors, or radiation therapy: used in the 6 months preceding the first trial vaccination, and up to the last blood draw.

Category 2 medications will be reported in the CRB according to the collection period detailed above up to the last blood draw.

- Category 3: Antibiotics that the subject received within 72 hours preceding each visit for blood draw related to IMP assessment (meningococcal vaccines) and used to define the PPAS. Category 3 medications will be reported in the CRB for the period of 3 days (72 hours) before each blood draw.

Note: Topical antibiotics (inhaled, otic, ophthalmic, nasal, etc.) should not be captured or reported.

The information reported in the CRB for each reported medication will be limited to:

- Trade name
- Rationale for the origin of prescription: Whether it was a prophylactic^a medication?
Prophylactic medications will be recorded in the Action Taken section of the AE collection tables.
- Medication category (1, 2, or 3)
- Start and stop dates

Dosage and administration route, homeopathic medication, will not be recorded.

^a Medication(s) prescribed for preventing AE occurrence (e.g. paracetamol to reduce the risk of fever)

If the subject has received medications other than those listed in Categories 1, 2, and 3, the detailed information will be collected in the source documents only.

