*This call will be made 8 days after the respective vaccinations. If day 8 falls on a weekend or holiday, the telephone call may be made on the following business day. During this telephone call, the staff will find out whether the subject experienced any SAE and/or MAAE not yet reported, and will remind the subject's parent / guardian to continue using the diary card, to bring the diary card to the study center at the next visit, and to confirm the date and time of the next visit.

†Staff will contact the subjects' parent / guardian by telephone within the 14 day time period before Visit 3 to remind them about the forthcoming study visit. If the subject's participation in the study is discontinued, the information recorded on the diary card will be reviewed at this time and the diary card will be retrieved by the site.

‡Staff will contact the subject's parent/ guardian by telephone at 6 months (+ 30 days) after the last vaccination visit to identify the occurrence of any SAEs (including any AESIs) and MAAEs not yet reported

§At Visit 1, subjects must be at least 24 weeks of age (168 days, the minimum age for the final dose of hepatitis B vaccine in the vaccine series), and no more than 32 weeks of age (224 days, the maximum age for the 3rd dose of rotavirus vaccine administration).

**Physical examination should be performed as per routine standard of care. Temperature should be measured before vaccination and recorded in the source documents.

††Should a subject receive oral or injectable antibiotic therapy within 3 days prior to any blood draw, the investigator will postpone that blood draw until it has been 3 days since the subject last received oral or injectable antibiotic therapy. Postponement must still be within the timeframe for blood draw. If postponement would result in the sample collection falling outside of this timeframe, the blood sample should be collected without postponement, and it should be documented appropriately that the sample was taken less than 3 days after stopping antibiotic treatment.

††Blood sample will be drawn prior to vaccinations.

§§Blood sample at Visit 2 is applicable only to approximately the first 50% of the subjects in Group 1 and Group 2.

***Blood sample at Visit 3 is applicable only to the subjects in Group 1 and Group 2 who did not provide a blood sample at Visit 2 (approximately 50% of subjects in each group).

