4.1.2 Immunogenicity

4.1.2.1 Immunogenicity Endpoint

The primary endpoint for the evaluation of immunogenicity is:

Meningococcal serogroups A, C, Y, and W antibody titers measured by hSBA, before the first study vaccination (Visit 1) and 30 days after the second dose of MenACYW conjugate vaccine or MENVEO® (Group 1 vs Group 2)

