5.2.3.2 Per-Protocol Analysis Set 2 (PPAS2)

During the second year of life, the immunogenicity analyses for various antigens will be performed on serology obtained 30 days after the given antigen administration if blood collection is planned at that time.

PPAS2 will be a subset of FAS2. The subjects presenting with at least one of the following relevant protocol deviations will be excluded from the PPAS2:

- Subject did not meet all protocol-specified inclusion criteria or met at least one of the protocol-specified exclusion criteria
- Subject did not complete the vaccination schedule including the infant and the second year of the study:
 - Group 1 and Group 2: Up to 12-13 month vaccinations, including the infant schedule
 - Group 3 and Group 4: Up to 23 month vaccinations
- Subject received a vaccine other than the one that he / she was randomized to receive
- Preparation and / or administration of vaccine was not done as per-protocol
- Subject did not receive vaccine in the proper time window
 - Group 1 and Group 2
 - Visit 3: 12 to 13 months of age
 - Group 3 and Group 4
 - Visit 2: 20 to 23 months of age
- Subject did not provide a post-dose serology sample in the proper time window or a post-dose serology sample was not drawn
 - Group 1 and Group 2
 - Blood Sampling 0003: Visit 4 (Visit 3 + 30 days [± 21 days])
 - Group 3 and Group 4
 - Blood Sampling 0002: Visit 3 (Visit 2 + 30 days [± 21 days])

- Subject received a protocol-prohibited therapy / medication / vaccine (reportable concomitant medication of category 2 and / or category 3)
- Subject had other protocol violations that affected the subject's immune response, as determined by the clinical team before locking the database

In addition to the reasons listed above, subjects will also be excluded from the PPAS if their serology sample did not produce a valid test result (i.e., results for all antigens are missing).

Vaccine correctness required by the PPAS2 includes not only the 2 doses of MenACYW conjugate vaccine, MENVEO®, or Menactra® but also, for subjects in groups 1 and 2, the concomitant vaccines (MMR, Varicella) as scheduled in the second year of life.

In the event of a local or national immunization program with a pandemic influenza vaccine or coronavirus vaccine, subjects who receive 1 or more doses of a pandemic influenza vaccine or coronavirus vaccine at any time during the study will not be withdrawn from the study.

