5.7 Changes in the Conduct of the Trial or Planned Analyses

For MET61 study, concomitant medications category fields were inactivated, and concomitant medications were coded with WHODrug dictionary by the coding specialists.

Two additional population analysis sets for persistence immunogenicity analysis after infant vaccination (FAS3 and PPAS3) and the corresponding definitions were added as those populations of analysis were not pre-defined in the protocol.

Sections 4.4.2.2.3, 4.4.2.2.4 and 5.3.1.4 were updated according to new version of the Standard Safety Tables.

6 References List

- 1 Newcombe R.G., Two-sided confidence intervals for the single proportion: comparison of seven methods, *Statistics in Medicine*, (1998) 17, 857-872
- 2 Newcombe RG. Interval Estimation for the difference between independent proportions: comparison of eleven methods. *Stat Med*. 1998; 17(8):873-90

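### Does the PPAS2 antibiotic exclusion remove children from the primary analysis because of a blood sample that analysis does not use?

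*SAP*

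**What the plan says.** Immunogenicity is analysed on the per-protocol sets. PPAS1 serves the sample 30 days after dose 1, PPAS3 (added in the SAP) the sample before dose 2, and PPAS2 the sample 30 days after dose 2. The primary endpoint (SAP 4.1.2.1) uses titres "before the first study vaccination (Visit 1) and 30 days after the second dose of MenACYW conjugate vaccine" or comparator, that is, draws BL0001 and BL0003 in Groups 1 and 2.

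One PPAS2 exclusion in SAP 5.2.3.2 reads: "Subject received a protocol-prohibited therapy / medication / vaccine (reportable concomitant medication of category 2 and / or category 3". Protocol 12.2.3.2 has the same bullet. Protocol 6.7 defines category 3 as: "Antibiotics that the subject received within 72 hours preceding each visit for blood draw related to IMP assessment".

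Three other provisions bear on the point:

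- When antibiotics precede a draw, "the investigator will postpone that blood draw until it has been 3 days since the subject last received oral or injectable antibiotic therapy", unless that would miss the sampling window (SAP Table 3.3 footnote).
- Exclusion criterion 21 of the protocol already bars "Receipt of oral or injectable antibiotic therapy within 72 hours prior to the first blood draw".
- SAP 5.7 reports that "concomitant medications category fields were inactivated, and concomitant medications were coded with WHODrug dictionary by the coding specialists".

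**The concern.** Every Group 1 or 2 child is due three draws: BL0001 at Visit 1, one middle draw (BL0002A at Visit 2 for about half, BL0002B at Visit 3 for the rest), and BL0003 at Visit 4. The middle draw also measures meningococcal titres, so it falls within category 3. The PPAS2 bullet names no draw. Taken at its word, it drops a child with valid BL0001 and BL0003 titres because of antibiotics before a sample the primary endpoint never uses. That would be an avoidable exclusion after randomisation from the primary analysis of a non-inferiority trial, in which the full analysis set is only exploratory.

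The bullet also relies on categories whose fields were switched off, and the SAP prints no rule for deriving them from coded drugs. Two programmers could therefore, in principle, build different primary sets from the same data.

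**Working it through.** **1. Which draws the rule reaches (Groups 1 and 2)**

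| Draw | Used by primary endpoint | Antibiotics within 72 h before it |
|---|---|---|
| BL0001, Visit 1 | yes | already excluded by criterion 21 |
| BL0002A or BL0002B, Visit 2 or 3 | no | excluded from PPAS2 on the literal reading only |
| BL0003, Visit 4 | yes | excluded on either reading |

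The literal reading adds one window per child. If a share q of children has antibiotics in a given window, independently between windows, the loss rises from q to 1 − (1 − q)², an increase of q(1 − q). For q = 1% that is 0.99%. The documents give no value for q.

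**2. What SAP 5.2.3.2 says around the bullet**

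The section opens by basing PPAS2 on serology taken 30 days after the antigen is given in the second year of life. Its list is confined to relevant deviations, and its serology bullet names only BL0003 (Groups 1 and 2) and BL0002 (Groups 3 and 4). Separate sets exist for the two middle draws. The natural reading attaches a deviation at BL0002A to PPAS1 and one at BL0002B to PPAS3.

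**3. Whether the categories can be rebuilt**

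Protocol 6.7 lists the drug classes and time windows for category 2, limits category 3 to non-topical antibiotics and 72 hours, and has trade name and start and stop dates recorded. With WHODrug codes, those are the items a derivation needs. Dates also separate short from long corticosteroid courses.

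**4. The plan's own power figure**

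Inputs (SAP 5.5): 435 enrolled per arm, at most 40% non-evaluable, so 435 × 0.60 = 261; margin 0.10; seroresponse A 97.7%, C 97.8%, Y 93.3%, W 86.7%, taken as equal in both arms. The 2-sided 95% interval (SAP 5.1.1.2) makes each test one-sided at 0.025.

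Farrington–Manning: power = Φ[(0.10 − 1.96·SE₀)/SE₁], with SE₁ = √(2p(1 − p)/n). SE₀ uses the rates p̃₁ and p̃₂ fitted under a true difference of −0.10.

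- W: p̃ = 0.8027 and 0.9027, SE₀ = 0.03072, SE₁ = 0.02973, so Φ(1.339) = 0.910.
- Y: p̃ = 0.8579 and 0.9579, SE₀ = 0.02494, SE₁ = 0.02189, so Φ(2.336) = 0.990.
- A and C: 1.000 after rounding.
- Overall: 1.000 × 1.000 × 0.9903 × 0.9097 = 0.901.

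The plan states 100, 100, 99.0, 91.0 and 90.0, so its figures are reproduced.

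**5. Extra loss on the literal reading (assumed range)**

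Overall power, with n per arm in brackets:

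| Extra loss | From 40% non-evaluable | From 30% | From 20% |
|---|---|---|---|
| 0% | 0.901 (261) | 0.9425 (304) | 0.967 (348) |
| 1% | 0.897 (258) | 0.940 (301) | 0.966 (344) |
| 2% | 0.893 (255) | 0.938 (298) | 0.964 (341) |
| 5% | 0.882 (247) | 0.930 (289) | 0.959 (330) |
| 10% | 0.861 (234) | 0.916 (274) | 0.949 (313) |

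Each 1% lost from 261 costs about 0.4 points. Overall power first falls below 80% at 204 per arm, a further loss of 57/261 = 22%.

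**The case for a change.** The strongest case for a change is that the primary population should not depend on how a bullet is read. In the same list the serology bullet names its draws, while the medication bullet does not. The literal reading can also exclude a child who was handled exactly as planned, because the Table 3.3 footnote directs that the sample be taken despite recent antibiotics when waiting would miss the window. The SAP's PPAS1 and PPAS3 bullets drop the category reference that PPAS2 keeps, and SAP 5.7 does not explain the difference. Nor does a drug code alone settle every case: the line between immune modulators in categories 1 and 2 needs judgement, and route of administration is not recorded.

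What stands is that the scope and the derivation are unwritten. That does not make the primary result unsound:

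- The review before lock is blind (protocol 11.3) and includes statistical input (SAP 5.6), so scope and borderline drugs can be settled without knowledge of the arm.
- Topical antibiotics are not to be entered in the case report book, which limits the problem of the missing route.
- Nothing points to a difference between arms. Investigators, parents, the sponsor and laboratory staff are blinded. On schedule, the 72-hour window before the middle draw opens no earlier than day 30 − 3 = 27 after dose 1.
- Any such child with a valid result after dose 2 stays in FAS2, so a discrepancy between the sets would be visible.

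Even the strict reading is coherent. Protocol and SAP carry the same bullet, and dropping every child with a prohibited exposure is a defensible, if severe, per-protocol rule.

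**Conclusion.** No change to the plan follows. This is a gap that analysts fill sensibly: PPAS2 takes its scope from the sample it serves, and protocol 6.7 supplies what is needed to rebuild the categories.

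The number of children at stake cannot be computed. It should be small, because draws are postponed after antibiotics: Visit 2 allows 21 further days, and Visit 3 has no upper day limit beyond age 12 to 13 months. Cases arise mainly when the window would be missed or a site does not postpone.

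On the literal reading, an assumed extra loss of 1% to 5% costs 0.4 to 1.9 points of overall power from the planned worst case, and 1.2 points or less from the expected 20% to 30% non-evaluable. If the 40% allowance already covers these exclusions, as an allowance for all non-evaluable children would, there is no loss against the stated 90%.

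This conclusion assumes that the postponement rule is followed, that antibiotic use before the middle draw is similar in the two arms, and that the drug list and its windows are fixed before unblinding. It would need another look only if the blinded review showed many children excluded solely for antibiotics before Visit 2 or Visit 3.

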5.2.3.3 Per-Protocol Analysis Set 3 (PPAS3)

Serology obtained at Visit3 for immunogenicity analysis for persistence 6 months after infant vaccination in a subset of subjects (Groups 1 and 2).

PPAS3 will be a subset of FAS3. The subjects presenting with at least one of the following relevant protocol deviations will be excluded from the PPAS3:

- Subject did not meet all protocol-specified inclusion criteria or met at least one of the protocol-specified exclusion criteria
- Subject did not complete the vaccination schedule
- Subject received a vaccine other than the one that he / she was randomized to receive
- Preparation and / or administration of vaccine was not done as per-protocol
- Subject did not receive vaccine in the proper time window
 - Group 1 and Group 2
 - Visit 1: 24 to 32 weeks of age
- Subject did not provide a pre-dose 2 serology sample in the proper time window or a pre-dose 2 serology sample was not drawn at Visit 3
- The serology sample did not produce a valid test results at Visit 3 (i.e., results are missing)
- Subject received a protocol-prohibited therapy / medication / vaccine
- Subject had other protocol violations that affected the subject's immune response, as determined by the clinical team before locking the database.

Vaccine correctness required by the PPAS3 includes not only the dose of MenACYW conjugate vaccine or MENVEO® but also the concomitant vaccines (DTaP, IPV, Hib, PCV13, Rotavirus, hepatitis B) as scheduled.

In the event of a local or national immunization program with a pandemic influenza or coronavirus vaccine, subjects who receive 1 or more doses of a pandemic influenza or coronavirus vaccine at any time during the study will not be withdrawn from the study.

5.2.4 Populations Used in Analyses

The safety analysis will be performed on the Safety Analysis Set (SafAS, and SafAS1 through SafAS4). Subjects will be analyzed according to the vaccine(s) they actually received.

All immunogenicity analyses will be performed on the PPAS (PPAS1 or PPAS2 or PPAS3). Additional immunogenicity analyses will be performed for exploratory purposes on the FAS (FAS1 or FAS2 or FAS3). In the FAS, subjects will be analyzed by the vaccine group to which they were randomized.

5.2.5 Other Analysis Set(s)

Not applicable.

5.3 Handling of Missing Data and Outliers

5.3.1 Safety

No replacement will be done in all subject listings, partial and missing data will be clearly indicated as missing.

5.3.1.1 Immediate

For unsolicited systemic AEs, a missing response to the “Immediate” field is assumed to have occurred after the 30-minute surveillance period and will not be imputed.

